2. RATIONALE, OBJECTIVES, AND BENEFIT-RISK ASSESSMENT

2.1 RATIONALE FOR PERFORMING THE STUDY

The rationale of the GLORIA-AF Registry Program is described in [Section 1.4](#). Phase II and III of the GLORIA-AF Registry Program collect data on patients with newly diagnosed non-valvular AF, their treatments and outcomes in a real-world setting.

2.2 STUDY OBJECTIVES

2.2.1 Main Objective

The main objectives are:

- To investigate the patient characteristics influencing the choice of antithrombotic treatment for the prevention of stroke in non-valvular AF patients
- To collect real world data on important outcome events of antithrombotic treatments for the prevention of stroke.

2.3 BENEFIT-RISK ASSESSMENT

As in any observational study, patients will be managed according to local medical practice. The choice of treatment is solely at the discretion of the participating physicians. This means there are no additional risks to patients by participating in this registry. No additional medical procedures are required, over and above those that the patient would receive if not enrolled.

Data from this Registry Program may contribute to the scientific knowledge regarding the management of patients with atrial fibrillation.

Proprietary confidential information.

© 2014 Boehringer Ingelheim International GmbH or one or more of its affiliated companies. All rights reserved.

This document may not - in full or in part - be passed on, reproduced, published or otherwise used without prior written permission.

3. DESCRIPTION OF DESIGN AND STUDY POPULATION

3.1 OVERALL DESIGN AND PLAN

GLORIA-AF Phase II/III is part of a global, multi-center, prospective Registry Program investigating patients with newly diagnosed non-valvular AF at risk for stroke (defined as a CHA₂DS₂-VASc stroke risk score of at least 1). Phase I (data collection before approval of dabigatran) of this Registry Program is described elsewhere ([U11-1009-02](#)). Phase II/III is outlined in three separate protocols: The present core protocol covering all global regions participating in Phase II and III of the Registry Program (1160.129, [U11-1638-03](#)) and two protocols with focus on the EU/EEA-member states (1160.136), as well as India (substudy 1160.171). The main design features within the protocols are identical and the analysis of the global study (1160.129) will also contain the data collected in patients entered in the present substudies (1160.136 and 1160.171).

Phase II, which is planned to be initiated after approval of dabigatran in the respective country consists of a baseline visit and a two-year follow-up for patients treated with dabigatran for the prevention of stroke. Thus, data on the use of dabigatran in routine clinical practice will be collected to describe how dabigatran is prescribed and used in the population of newly diagnosed non-valvular AF patients and how these factors influence important outcome and safety events. In addition, compliance with the dabigatran SmPC with regards to indication, posology, contraindications and warnings will be evaluated. The utilization of dabigatran will be assessed with regards to treatment persistence, compliance, proportion of patients discontinuing treatment and reason for discontinuation. Patients enrolled in Phase II initially receiving other oral anticoagulants than dabigatran (e.g. VKAs) or antithrombotic therapy, or no therapy for stroke prevention, will only participate in the baseline visit without participation in any subsequent follow-up visits.

Before initiation of Phase III, regular interim analyses will be conducted during Phase II on patients initiating dabigatran and those initiating VKA at the baseline visit to evaluate the similarity of patients in these two groups. These interim analyses will occur on a regional basis, based on the number of patients enrolled (approximately once or twice a year). Once comparability regarding important baseline characteristics (known risk factors for stroke and bleeding e.g. age, gender, hypertension, diabetes mellitus, prior stroke, prior transient ischemic attack, prior bleeding and concomitant medication use) of these groups has been established and the likely amount of residual channeling bias after confounder adjustment is comparatively small, Phase III will be initiated. The main measure to determine comparability of the two treatment groups regarding their important baseline characteristics will be the overlap on the propensity score, as measured by the proportion of patients in the region of overlap of the propensity score. Patients already enrolled in Phase II will complete their visit schedule as planned. Each patient enrolled into GLORIA-AF can only participate in one phase, i.e. those patients enrolled into Phase II are not eligible to participate in Phase III. In Phase III all newly diagnosed non-valvular AF patients will be followed up for three years regardless of antithrombotic therapy treatment status.

It could turn out that Phase III cannot be conducted in the EU region; i.e. if after two years of assessing baseline characteristics of dabigatran and VKA initiators in Phase II comparability

Proprietary confidential information.

© 2014 Boehringer Ingelheim International GmbH or one or more of its affiliated companies. All rights reserved.

This document may not - in full or in part - be passed on, reproduced, published or otherwise used without prior written permission.

has not been achieved, which would preclude any meaningful comparisons, then one of the following three scenarios to assess long-term comparative outcomes will be pursued:

1. If substantial overlap is achieved, and comparability in Phase II is expected to be achieved within the following six months, i.e. overlap is expected to be very soon sufficient, then Phase II will be prolonged for six more months before entering Phase III.
2. If some overlap is achieved, but comparability is expected not to be achievable in Phase II within the following six months due to persistent channeling bias, then Phase III will be started and a matched analysis will be conducted, being aware of the draw back that the power could not be sufficient for all outcomes.
3. If little or no overlap is achieved, and it appears highly unlikely that comparability would be achievable even if the study were extended for a prolonged period of time as significant channeling bias persists, then a separate database study based on existing data (e.g. claims data, electronic medical records) on long-term outcomes will be initiated to ensure sufficient power within matched cohorts.

The variables that will be considered for matching in scenario 2 and 3 will consist of a subset of those that were used for the assessment of comparability. Their choice will be based on the strength of the association of those variables with the outcome under study and the learnings from the interim results. At least age and gender will be matching variables. In addition, scores derived from those variables (e.g. the estimated propensity score) could be considered as a matching variable.

The study described in this protocol will collect data in up to 23 European countries (for planned participating countries see [Appendix 10.3](#)) in up to about 680 sites and is planned to involve as many as 2,000 investigators. It is planned to enroll approximately 5,000 patients in Phase II and another 10,000 patients in Phase III.

The planned registry period is from July 2011 to June 2020, which covers the total expected duration of Phase II and III.

Enrollment into Phase III of the global study will end after the overall enrollment goal has been met, or by June 2017, whichever comes first. Individual regions may end earlier depending on recruitment.

3.1.1 Administrative structure of the study

Steering Committee

A Steering Committee will provide scientific leadership for the planning and conduct of all phases of the Registry Program. It will be composed of experts in cardiology, vascular medicine, neurology and epidemiology with one Chair and Co-Chair as well as representatives of the Sponsor. A charter describing the tasks and responsibility of the committee will be developed. Membership in the Steering Committee may change over time for various reasons.

Proprietary confidential information.

© 2014 Boehringer Ingelheim International GmbH or one or more of its affiliated companies. All rights reserved.

This document may not - in full or in part - be passed on, reproduced, published or otherwise used without prior written permission.

Operations Committee

The study conduct will be overseen by an Operations Committee (OC), consisting of the Chair, Co-Chair, the epidemiologist of the Steering Committee and representatives of the sponsor. The Operations Committee will oversee the execution of the Registry Program and, in conjunction with the SC, facilitate the publications. Membership in the Operations Committee may change over time. In Phase II, the OC will evaluate the results of the periodic analyses of the patient baseline characteristics which will determine the initiation of Phase III of the Registry Program. In Phase III, the OC will continue to evaluate the results of periodic interim analyses to compare the baseline characteristics of patients initiating dabigatran or VKAs. The number of members can be changed if warranted. A charter of the Operations Committee will be developed.

The OC will meet regularly, based upon the volume of work. Meetings will generally be by teleconference or web-conference. Face-to-face meetings may occasionally be held if there is a necessity.

3.2 DISCUSSION OF STUDY DESIGN, INCLUDING THE CHOICE OF CONTROL GROUP(S)

The registry includes newly diagnosed non-valvular AF patients at risk for stroke. This permits comparison of treatment initiators and facilitates correct adjustment for predictors of treatment rather than for consequences of treatments (intermediates). In addition, this allows for the assessment of treatment hazards over time and avoids the inclusion of prevalent users of anticoagulants who are potentially healthier and less susceptible to adverse outcomes (so called “VKA survivors”) compared to new users ([R11-2308](#)).

Furthermore, the assessments of channeling bias in Phase II will allow for collecting longitudinal data on patients starting dabigatran and VKA only after they are deemed comparable regarding their important baseline characteristics, and thus reduce the potential for biased comparisons in Phase III. However, if comparability of baseline characteristics is insufficient, alternative approaches will be followed to assess long-term outcomes ([see section 3.1](#)).

3.2.1 Potential for bias and confounding

Selection bias

Selection bias may occur on two different levels: The site level and the patient level. If sites where dabigatran is most used differ systematically with respect to patients or routine procedures from sites in which it is less used, the between-site difference would lead to noncomparability between dabigatran patients and others, even if no clinician accounted for patient characteristics in his or her decision to use the product.

To minimize selection bias at the site level, the goal is to have participating centers reflect a (country specific) balance between general practices, specialist offices, community hospitals, university hospitals, outpatient care centers and anticoagulation clinics. Basic characteristics

Proprietary confidential information.

© 2014 Boehringer Ingelheim International GmbH or one or more of its affiliated companies. All rights reserved.

This document may not - in full or in part - be passed on, reproduced, published or otherwise used without prior written permission.

of sites that did not participate will be summarized.

Selection bias at the patient level might occur if for example, sites preferentially reported "interesting" cases to the Registry, and particularly if they did so differently for initiators of dabigatran and VKAs. To minimize selection bias at the patient level, consecutive patients from each site who meet entry criteria of this Registry Program are expected to be invited to participate in the registry.

Consecutive enrollment of patients to avoid selection bias should be emphasized. As participation in another international registry is an exclusion criteria for entry into the study (please refer to section 3.3.3), parallel enrollment in another international registry on the use of oral anticoagulation in AF in the same department should be avoided, as otherwise consecutive enrollment would be challenging. In addition, it should be ensured that both dabigatran and VKAs are available at participating sites or that availability for both treatment options is foreseen in the near future. In the latter case, information on treatment availability has to be documented.

Loss to follow up

All efforts will be made to minimize loss to follow up in patients with a pre-planned follow up (such as patients initiating dabigatran in Phase II and all patients in Phase III), particularly in the assessment. Also, patients lost to follow up will be characterized compared to the remaining patients and reason and time point of loss to follow up will be evaluated.

Channeling bias

Channeling bias can occur due to preferential prescribing in relation to different risks for the events of interest: e.g., if dabigatran would be more often prescribed to higher risk patients compared to other treatments, higher incidences of outcome events were then expected in the dabigatran group. The potential for channeling bias will be reduced due to the two phase design of the Registry Program and will be assessed throughout the study. The assumption is that some channeling bias may occur in the immediate post-approval period, but will not persist; therefore periodic assessment of choice of treatment in relation to the patients' important baseline characteristics will allow appropriate timing of initiating Phase III. However, if comparability of baseline characteristics is insufficient, alternative approaches will be followed to assess long-term outcomes ([see section 3.1](#)). In order to control for potential channeling bias after approval of dabigatran, regular assessments will be conducted, i.e. patients initiating VKAs and dabigatran will be assessed regarding the comparability of important patient baseline characteristics (known risk factors for stroke and bleeding, e.g. age, gender, hypertension, diabetes mellitus, prior stroke, prior transient ischemic attack, prior bleeding and concomitant medication use). Further comparisons of drugs may be added in order to reflect the possible approval of other new oral anticoagulants. This will be performed within regions. Details of the decision process for triggering the start of Phase III will be described in the Statistical and Epidemiological Analysis Plan (SEAP).

Depletion of susceptibles and healthy user/ adherence bias

Proprietary confidential information.

© 2014 Boehringer Ingelheim International GmbH or one or more of its affiliated companies. All rights reserved.

This document may not - in full or in part - be passed on, reproduced, published or otherwise used without prior written permission.

Depletion of susceptibles occurs, when persons most at risk for an event suffer the event early on in therapy, so that cohorts ascertained later in therapy have a lower prevalence than such at risk patients. In the absence of a direct measure of susceptibility, depletion of susceptibles manifests itself as an apparently declining risk with the passage of time. Other common reasons for a risk that decline with time elapsed since initiation of therapy include metabolic adaptations that diminish the effect of the product (tachyphylaxis) and the prescriber's acquisition of skill in managing the drug for a particular patient. Whatever the origin, when the risk of an outcome varies over time especially when the risk is higher just after initiating therapy and declines thereafter, the comparison of prevalent users and incident (new) users will be biased, because long-time users will be less likely to manifest the outcome of interest. In addition, there is potential healthy user / adherence bias, which is that patients who use a drug or are adherent with treatment are more likely to be healthier in general (e.g. have other healthy behaviors) than patients who are non-user/non-adherent. The effects of changes in risk with time and adherence will be mitigated through the use of initiator cohorts and will be assessed through an intention to treat sensitivity analysis. Only newly diagnosed AF patients initiating antithrombotic treatment at baseline will be included throughout the Registry Program. To account for time varying risks, estimates of cumulative risks will be calculated.

Information and recall bias

Information bias can occur for example, due to selective under-reporting of already established and known adverse effects for a known product (VKA) as compared to a new product (dabigatran), or vice versa. A standardized data collection form will be used for assessing exposure and AEs (see [Section 6](#)). Medical charts will also be reviewed by site staff and during CRA monitoring visits. These standardized procedures for data collection are intended to minimize such biases. Recall bias may be caused, e.g. if visits are separated by long time intervals and patients forget certain information (e.g. use of over-the-counter medications). It can be reduced by associating questions with specified time intervals (e.g. how often did you take this co-medication during the last 7 days?).

Confounding

As in any observational study, confounding may affect the estimation of association between drug exposure and outcome of interest and statistical techniques such as adjustment for covariates, stratified analyses, matching, etc. can be used to correct for these. But as only major confounders for selected research questions can be captured, residual (unmeasured) confounding may remain.

3.3 SELECTION OF POPULATION

Regarding the consecutive enrollment of patients, please refer to [Section 3.2.1](#).

3.3.1 Main diagnosis for study entry

Patients with newly diagnosed non-valvular AF (documented by 12 lead ECG, ECG rhythm strip, pacemaker/ICD electrocardiogram, or Holter ECG) less than 3 months before the patient's baseline visit will be included. Each patient must be at risk for stroke with one or

Proprietary confidential information.

© 2014 Boehringer Ingelheim International GmbH or one or more of its affiliated companies. All rights reserved.

This document may not - in full or in part - be passed on, reproduced, published or otherwise used without prior written permission.

more risk factors, as defined by a CHA₂DS₂-VASc stroke risk score of at least 1 (see [Table 10.1: 2](#))

3.3.2 Inclusion criteria

1. Age ≥ 18 years at enrollment
2. Male or female patient (or legally acceptable representative) willing and able to provide written informed consent
3. Patient newly diagnosed (< 3 months prior to baseline visit) with non-valvular AF. Documentation of AF by 12 lead ECG, ECG rhythm strip, pacemaker/ICD electrocardiogram, or Holter ECG (duration of AF episode at least 30 seconds) needed for all enrolled patients.
4. Patient must have a CHA₂DS₂-VASc score of at least 1 (see [Table 10.1: 2](#)). This requires the presence of at least one of the following risk factors:
 - a. Congestive heart failure (NYHA Class 2 or greater) or moderate to severe LV systolic dysfunction (e.g. LV EF $\leq 40\%$)
 - b. History of hypertension or systolic blood pressure >160 mmHg
 - c. Diabetes mellitus
 - d. History of stroke, transient ischemic attack, or systemic embolism
 - e. Vascular disease defined as prior myocardial infarction, peripheral artery disease, complex aortic plaque
 - f. Age ≥ 65
 - g. Female gender

Although AF diagnosis is a baseline requirement, patients are not required to have an ongoing AF episode at the time of entry into this Registry Program.

3.3.3 Exclusion criteria

1. Presence of any mechanical heart valve, or valve disease that is expected to require valve replacement intervention (surgical or non-surgical) during the course of the assigned registry phase.
2. Patients who have received more than 60 days of VKA treatment in their lifetime prior to the patient's baseline visit
3. AF with a generally reversible cause (e.g., cardiac surgery, pulmonary embolism, untreated hyperthyroidism)

Proprietary confidential information.

© 2014 Boehringer Ingelheim International GmbH or one or more of its affiliated companies. All rights reserved.

This document may not - in full or in part - be passed on, reproduced, published or otherwise used without prior written permission.

4. Patient's life-expectancy is expected to be less than one year at the time of potential enrollment as assessed by the investigator
5. Patients with a medical condition other than atrial fibrillation for which chronic use of an oral anticoagulant (for example, a VKA) is indicated
6. Current participation in any clinical trial of a drug or device
7. Current participation in an international registry on the use of oral anticoagulation in AF
8. Patient was enrolled in any other phase of the GLORIA-AF Program.
9. Patient with no further follow-up possible with enrolling investigator during planned study period (such as anticipated relocation).

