6.1.2 Specification of treatments for analyses

Reference time periods for the analysis of outcome events, exposure time, AEs are specified in the study protocol:

A patient is considered to have permanently stopped initial antithrombotic treatment according to the definition of antithrombotic treatment start and stop date provided in [Table 6.1.2:1](#).

For the main analysis (as treated analysis) of outcome events, patients will be grouped according to the therapy prescribed for long term treatment at baseline visit, excluding patients who never took the prescribed medication. This will be derived based on the CRF question on planned long-term AF treatment documented at baseline. The number and percentage of patients who never took the prescribed medication (defined as not taken one single dose of prescribed medication) will explicitly be shown in the disposition table (see [Table 6.4:1](#)); they will be excluded from all main outcome analyses if they did not take the treatment group defining medication (e.g. a patient prescribed to VKA+Clopidogrel which took only VKA will be grouped as a VKA patient; a patient prescribed to VKA+Clopidogrel and took only Clopidogrel will be excluded from all main outcome analyses). For potential outcome analyses patients will be included under the treatment (mono/combi) and dose they

were prescribed and actually took. Start and end of initial treatment regimen episode which will be used as analysis period for the main analysis of outcome events are defined as follows:

Table 6.1.2: 1 Treatment regimen episode start and stop

Treatment group	initial treatment regimen episode start	initial treatment regimen episode stop
(Combinations with) NOAC_X* - excluding combinations with other (N)OACS:	
The NOAC treatment start date starts active medication;
 
 if NOAC treatment start date < min(date of ICF sign off, date of baseline visit) then use min(date of ICF sign off, date of baseline visit) instead if NOAC start date is missing then use date of ICF sign-off. 	minimum{ 
 permanent stop\$ date of NOAC+3days, start date of other chronic anticoagulant treatment (i.e. VKA, new oral anticoagulants other than original NOAC) -1day date of study completion/discontinuation }

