6.8 CALCULATION OF TIME TO EVENTS OR CENSORING

The derivations of time to event and time to censoring for the time to event analyses are specified in this section. The information from the outcome event pages will be used to collect events. Deaths reported via the vital status or serious adverse event page will also be included.

Events to be counted in the study period are all events with onset date \leq patient’s study termination date. Events occurring after the patient’s study termination date will NOT be included in the analysis (irrespective of whether they occur during the washout period or later) as treatment information will in general not be documented in the CRF for this time period. The event death is an exception. Death captured via the vital status page will still be considered after the patient’s discontinuation.

For composite outcome events, the onset date of the first occurring component event will be used.

The following rules will be used for the main analysis of outcome events:

The analysis will be based on the antithrombotic treatment choice selected at baseline (long-term treatment information, as collected in the following CRF question: “Please report any antithrombotic treatments that you prescribed for long term use at the time of the baseline visit, or any antithrombotic treatments that the patient was already on at the time of the baseline visit that the patient will remain on for long term use”) and the initial treatment regimen episode (as specified in [Section 6.1.2](#)). An event will be counted for the main analysis if it occurs during the initial treatment regimen episode of the antithrombotic therapy selected at baseline.

The time to event will be calculated as: event date - initial treatment regimen episode start date + 1.

The time to censoring will be calculated as initial treatment regimen episode stop date - initial treatment regimen episode start date + 1 (as described in [Table 6.1.2:1](#)).

Patients participating in a clinical trial with a drug or device or in another international drug study or registry on the use of oral anticoagulation in AF will be censored when they enter the trial/study. The exception is with clinical studies of idarucizumab (Praxbind) where explicit provision for collection of this data has now been included.

The following rules will be used for the intention-to-treat analysis of outcome events :

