Patients who discontinue initial antithrombotic treatment for stroke prevention permanently will be censored at date of last drug intake + 3 days (for dabigatran and non-VKA treatments) and +6 days (for VKA treatment or combinations of VKA with other antithrombotic treatments) or at first intake of other relevant chronic antithrombotic treatment for stroke prevention, whichever comes first (unless the event occurred prior to the time of censoring). A patient is considered to have permanently stopped initial antithrombotic treatment for stroke prevention, if another relevant chronic antithrombotic treatment is initiated for stroke prevention (switch) or depending on the duration of treatment interruption (see [Section 6.1.2](#)). Treatment effects and subgroup variable effects will be reported.

Multiple imputation methods (e.g. the fully conditional specification method) will be used to impute both continuous and categorical variables appropriately with arbitrary missing patterns. Each single step of the variable selection procedure above should be based on the combined estimates of the parameter estimates from all the models using the multiple imputed datasets.

- 2) Sensitivity analyses for composite outcome (Stroke, systemic embolism, myocardial infarction, life-threatening bleeding events and vascular death)

For 1160.136, only the sensitivity analyses on the ITT approach (d) and the sensitivity analyses on other multivariate models (f) will be performed.

- a. **The primary sensitivity analysis** for the comparison between dabigatran and VKA treatment groups in terms of the composite outcome of stroke, SEE, vascular death, MI, life-threatening bleeds will be a **stratified analysis based on propensity scores and stratified by region**. For the stratification process the PS will be categorized by e.g. deciles or quintiles based on the smaller treatment group and depending on the number of patients per region. A Cox model with treatment as the only independent variable will be used. The stratified results will be combined to end up with one final effect estimate.

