consecutive physical visit (censoring date will be the last physical visit prior to the consecutive telephone/missed visits). In addition, patients who had their last study visit as telephone visit will be censored at their last physical visit. An event will only be counted for this analysis if it occurs during the initial treatment regimen episode of the antithrombotic therapy selected at baseline (as defined in [Section 6.1.2](#)) and prior to the time point of censoring. Start dates for calculation of time to event and time to censoring are defined as for the main analysis.

- f. In order to explore which factors potentially modify the effect of dabigatran vs. VKA in terms of occurrence of the composite outcome, additional interaction terms (treatment*(factor potentially impacting safety and effectiveness)) might be included in multivariable regression models similar to the final main model. Factors to be explored include stroke risk factors as those might impact safety and effectiveness of dabigatran. Forest plots will be used to graphically summarize the treatment effects in the different subgroups.
- g. Another sensitivity analysis on the main model might be performed using treatment-naïve patients only, i.e. patients without any OAC treatment within the last 3 months prior to the baseline visit.
- h. An imputation method similar to Phase II for the multivariable regression analyses might be performed on the main model. Missing information on risk factor variables (binary variables) with a frequency (prevalence) below 50% in patients with data will be treated as absence of risk factor. Missing information on intake of co-medication at baseline will be considered as no intake of the co-medication. The risk scores (derived variables e.g. Has-Bled score) will be calculated from the (possibly imputed) components. For missing variables that have not been described as risk factors for stroke or major bleeding in the literature nor have a known impact on PK/PD of the treatments analyzed, a value will be randomly assigned based on the distribution of patients with values.
- i. To explore the impact of the primary imputation approach for unknown cause of death, the following two alternative approaches will be considered: (1) Unknown cause of death will be imputed as a vascular cause; (2) Unknown cause of death will be imputed as a non-vascular cause.

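### The dabigatran and VKA cohorts are not restricted to initiators, prior users' clocks restart at enrolment, and for 1160.136 no guaranteed analysis tests the effect

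*Protocol*

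**What the plan says.** **The design claim.** Protocol 3.2.1, on depletion of susceptibles, says: "Only newly diagnosed AF patients initiating antithrombotic treatment at baseline will be included throughout the Registry Program". Protocol 3.2 says that enrolling newly diagnosed patients "avoids the inclusion of prevalent users of anticoagulants".

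**The entry criteria.** Exclusion 2 in Protocol 3.3.3 removes "Patients who have received more than 60 days of VKA treatment in their lifetime prior to the" baseline visit. No criterion limits earlier dabigatran or other NOAC use. The nearest one, Exclusion 5, concerns a different group: "Patients with a medical condition other than atrial fibrillation for which chronic use of an oral anticoagulant (for example, a VKA) is indicated". The SAP's list of important violations (Table 6.2:1) has a code for prevalent warfarin use and none for NOACs. For AF treatment, the only bound on earlier dabigatran is inclusion criterion 3: diagnosis less than 3 months before baseline. For the Latin American region, Table 6.2:1 flags a violation only from 4.5 months.

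**Index treatment and time zero.** The CRF question in SAP 6.8 that defines the index treatment includes "any antithrombotic treatments that the patient was already on at the time of the baseline visit". SAP Table 6.1.2:1 then sets the clock: "if NOAC treatment start date < min(date of ICF sign off, date of baseline visit) then use min(date of ICF sign off", or the baseline visit date if that is earlier. The VKA row has the same rule. SAP 6.8 uses this start date for the ITT analysis as well.

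**Safeguards in SAP 7.6.** OAC pre-treatment is tabulated at baseline. Previous OAC use within 3 months is a candidate covariate, not a core one, and enters only if it moves the hazard ratio by more than 10%. Sensitivity analysis (g), in "patients without any OAC treatment within the last 3 months prior to the baseline visit", is worded as something that might be done. For 1160.136, "only the sensitivity analyses on the ITT approach (d) and the sensitivity analyses on other multivariate models (f) will be performed".

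**The concern.** Time zero is not treatment start for every patient. Someone who has taken dabigatran for 80 days without an event can enter the Cox risk set at day 1 beside someone taking a first VKA tablet. Events and discontinuations before enrolment are not seen. Protocol 3.2.1 itself explains that when risk is highest just after initiation, comparing established users with new users is biased, and it relies on initiator cohorts and an ITT analysis to deal with this. The cohorts are not limited to initiators, and the ITT analysis shares the reset origin, so it cannot correct it.

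The longest permitted earlier exposure also differs between the arms. At stake are the early event rates in each arm, including the category up to 3 months in the planned Kaplan-Meier tables, and the dabigatran-VKA hazard ratio.

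**Working it through.** **1. Attrition model, checked against the protocol.** Protocol 7.6 assumes 25% per year discontinuation and loss. Exponential attrition gives patient-years = N × (1 − 0.75^T) / (−ln 0.75).
- Phase III: 2,000 × (1 − 0.75³) / 0.2877 = 4,019 (stated 4,019).
- Phase II: 2,500 × (1 − 0.75²) / 0.2877 = 3,802 (stated 3,802).

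**2. Permitted exposure before the clock starts.** VKA: 60 days. Dabigatran for AF: just under 3 months, about 91 days. The gap is about 31 days. At 25% per year, 1 − 0.75^(60/365.25) = 4.6% of initiators would have stopped or been lost by day 60, and 6.9% by day 91.

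**3. Illustration of the bias.** Apart from the attrition rate, these inputs are assumptions, not document figures:
- true hazard ratio 1;
- hazard k times the later hazard for the first 90 days on drug, k = 1.5 to 3;
- prior users enter at day 75 (dabigatran) or day 45 (VKA);
- prior users are 20% to 60% of each arm.

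Let P(t) be expected follow-up days per patient up to day t: P(t) = (1 − 0.75^(t/365.25)) / (0.2877/365.25). Then P(15) = 14.9, P(45) = 44.2, P(90) = 86.9 and P(1095) = 733.7.

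The 3-year rate, relative to the later hazard, for a patient entering at day s of therapy is R(s) = 1 + (k − 1) × P(90 − s) / P(1095):
- new starter: 1 + 0.1184 (k − 1)
- dabigatran prior user: 1 + 0.0203 (k − 1)
- VKA prior user: 1 + 0.0603 (k − 1)

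An arm with share f of prior users has rate f × R(s) + (1 − f) × R(0). For k = 2 and f = 40% in both arms:
- dabigatran: 0.4 × 1.0203 + 0.6 × 1.1184 = 1.079
- VKA: 0.4 × 1.0603 + 0.6 × 1.1184 = 1.095
- ratio: 0.985

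Apparent 3-year dabigatran/VKA rate ratio when the truth is 1:

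| Prior users, dabigatran / VKA | k = 1.5 | k = 2 | k = 3 |
|---|---|---|---|
| 20% / 20% | 0.996 | 0.993 | 0.987 |
| 40% / 40% | 0.992 | 0.985 | 0.973 |
| 60% / 60% | 0.988 | 0.978 | 0.959 |
| 20% / 60% | 1.007 | 1.014 | 1.026 |
| 60% / 20% | 0.978 | 0.957 | 0.922 |

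**4. Early rates.** Replacing P(1095) by P(90), with equal shares of 20% to 60%, the first-90-day rate is understated by 6% to 33% for dabigatran and by 3% to 20% for VKA.

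**5. Would the 10% rule bring in previous OAC use?** The largest 3-year distortion in the table is 1 − 0.922 = 7.8%, and with equal shares it is 4.1%. Removing a bias of that size would not by itself move the hazard ratio by more than 10%. The covariate could still enter for other reasons, but the rule does not ensure it. A yes/no flag also does not restore the true start date.

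**The case against.** **A reader might infer that the gap favours dabigatran**, because its permitted run-in is longer. The documents do not support that. A ceiling is not an observed exposure, and with 20% prior users on dabigatran against 60% on VKA the false ratio lies above 1.

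**A reader might also lead with the first 90 days**, where equal shares give a false ratio of 0.98 to 0.83 (1.05 to 1.11 with 20% against 60%). But the planned comparison is a Cox model over the whole initial treatment episode; results by interval are descriptive.

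**Nor can one say that these are not initiator cohorts at all.** Some patients may be prior users; how many is unknown. The worry in Protocol 3.2 is long-term VKA survivors, and the 60-day cap with the diagnosis window does keep those out. The real conflict is with the sentence in 3.2.1 about starting at baseline.

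Other points on that side stand. The reset applies to both arms. The 75 and 45 days are near the ceilings: spreading earlier exposure evenly over 0–91 and 0–60 days, with equal shares, brings the 3-year ratio to between 0.998 and about 0.98. Sampling error is larger: 4,019 patient-years at 3 per 100 give about 120 events per arm, so the 95% limits on a hazard ratio are a factor of about exp(1.96 × √(2/120)) = 1.29 either way. The pre-treatment tables will show the share of prior users, and the propensity model is in a separate plan not available here, so its handling of earlier OAC use is unknown.

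None of this corrects time zero or guarantees a test of its effect. Wide intervals do not excuse a systematic error that collected data can examine.

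**Conclusion.** The point holds in limited form. The cohorts are not restricted to initiators, contrary to Protocol 3.2.1, and the start-date reset hides earlier time on drug in the main and ITT analyses alike. If early hazard is raised, early rates are understated in both arms and the hazard ratio can be biased in either direction.

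Under the stated assumptions the 3-year distortion is about 0.4% to 4% with equal shares and about 1% to 3% the other way with 20% against 60%; the reverse imbalance, 60% against 20%, gives 2% to 8%. It rests on two quantities that the documents do not give: the early-hazard multiplier and each arm's share of prior users.

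This is a should-fix. The text conflict is certain; the existence, size and sign of any bias are not. The gap in the plan is clearest for 1160.136, where (g) is not among the sensitivity analyses kept.

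**What to change.** In SAP 7.6:
1. Make treatment-naive analysis (g) mandatory, and add it to the 1160.136 list. This tests the concern most directly.
2. Move previous OAC use (within 3 months) from the candidate covariates to the core set.
3. Add one sensitivity analysis: a Cox model on time since the recorded start of the index OAC, with delayed entry at baseline. Alternatively, analyse a set with the same 60-day limit on prior use in both arms. Delayed entry compares patients at equal time on drug; it does not recover events before enrolment. Changing the main time scale is not needed.

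The report should describe the cohorts as newly diagnosed patients with limited earlier OAC use, not as initiators only.

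**Cost.** SAP wording and programming. Protocol 6.2.1 already collects antithrombotic start dates at baseline. The restricted sets are smaller and give wider intervals. The core covariate uses one degree of freedom, which is 10 events under the SAP's overfitting rule. Patients with a missing start date cannot be re-timed.
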